| Figure GPHD.5.1. | Illustration of study design for clinical protocol I8F-MC-GPHD..... | 13 |
| Figure GPHD.5.2. | Flowchart to ascertain need for insulin glargine (U100) optimization..... | 15 |
| Figure GPHD.6.1. | Type 1 Error control strategy for primary and key secondary efficacy endpoints..... | 29 |

Table of Contents

| Appendix | | Page |
|-----------------|--|-------------|
| Appendix 1. | Searching Criteria for Adverse Events of Special Interest..... | 50 |

3. Revision History

The first version of the statistical analysis plan (SAP) was approved prior to First Patient Visit (FPV).

The second version is approved before the final database lock. The following represent major changes made for the second version:

1. Updated definition of analysis set. For consistency with SURPASS 1-5 trials, exclude patients discontinuing study drug due to inadvertent enrollment from efficacy analyses.
2. Updated baseline definition as time is not collected in GPHD eCRF.
3. Missing data imputation: Modified the definition of “retrieved dropouts”.
4. Updated analysis used for hemoglobin A1c (HbA1c) and weight loss threshold analyses.
5. Change in alpha recycling for type 1 error rate control.
6. Removed ‘The patient recovered/ resolved with sequelae’ from Severe hypoglycemia requiring hospitalization, documented medical help, or is life threatening as this criteria alone will not be sufficient to meet additional criteria.
7. Removed section on Anti-Drug Antibodies as it was not collected for all patients.
8. Added section to assess SARS-CoV-2 (COVID-19) impact.

4. Study Objectives

4.1. Primary Objectives

The primary objective of the study is to demonstrate noninferiority of tirzepatide pooled cohort of 5 mg, 10 mg, and 15 mg once weekly (QW) versus insulin lispro (U100) three times a day (TID), when added to insulin glargine (U100), with or without metformin, with respect to mean change in hemoglobin A1c (HbA1c) from baseline at 52 weeks.

4.2. Key Secondary Objectives Subject to Strong Type 1 Error Rate Control

Together with the primary objective, the following secondary objectives are subject to strong control of the type 1 error rate (see Section 6.12.3):

- To demonstrate superiority of tirzepatide pooled cohort of 5 mg, 10 mg, and 15 mg QW versus insulin lispro (U100) TID, when added to insulin glargine (U100), with or without metformin at 52 weeks for
 - mean change in HbA1c from baseline
 - mean change in body weight from baseline, and
 - proportion of participants with HbA1c target values of <7.0% (53 mmol/mol).
- To demonstrate noninferiority of tirzepatide 5 mg, 10 mg, and/or 15 mg QW versus insulin lispro (U100) TID, when added to insulin glargine (U100), with or without metformin at 52 weeks for
 - mean change in HbA1c from baseline.
- To demonstrate superiority of tirzepatide 5 mg, 10 mg, and/or 15 mg QW versus insulin lispro (U100) TID, when added to insulin glargine (U100), with or without metformin at 52 weeks for
 - mean change in HbA1c from baseline and
 - mean change in body weight from baseline.

4.3. Other Secondary and Exploratory Efficacy Objectives Not Subject to Type 1 Error Rate Control

The following secondary efficacy objectives are not subject to strong control of the type 1 error rate:

- To demonstrate that tirzepatide (pooled cohort of 5 mg, 10 mg, and 15 mg) QW is superior to insulin lispro (U100) TID, when added to insulin glargine (U100), with or without metformin at 52 weeks for:
 - proportion of participants achieving HbA1c target $\leq 6.5\%$ (48 mmol/mol)

- mean change in fasting serum glucose (central laboratory) from baseline
- mean change in daily average 7-point self-monitored blood glucose profiles from baseline
- proportion of participants who achieved HbA1c target value of $<7.0\%$ (53 mmol/mol) without hypoglycemia (confirmed glucose <54 mg/dL [3.0 mmol/L] or report of severe hypoglycemia)
- proportion of participants who achieved weight loss of $\geq 5\%$ from baseline. and
- mean change from randomization in Short Form-36 Health Survey (SF-36v2) acute form
 - Physical Component Summary score
 - Mental Component Summary score
 - Physical Functioning domain score
 - General Health domain score
 - Vitality domain score
 - Role-Physical domain score
 - Bodily Pain domain score
 - Social Functioning domain score
 - Role-Emotional domain score
 - Mental Health domain score.
- To demonstrate that tirzepatide 5 mg, 10 mg, and/or 15 mg QW is superior to insulin lispro (U100) TID, when added to insulin glargine (U100), with or without metformin at 52 weeks for:
 - proportion of participants achieving HbA1c target $<7.0\%$ (53 mmol/mol)
 - proportion of participants achieving HbA1c target $\leq 6.5\%$ (48 mmol/mol)
 - mean change in fasting serum glucose (central laboratory) from baseline
 - mean change in daily average 7-point self-monitored blood glucose profiles from baseline
 - proportion of participants who achieved HbA1c target value of $<7.0\%$ (53 mmol/mol) without hypoglycemia (confirmed glucose <54 mg/dL [3.0 mmol/L] or report of severe hypoglycemia)
 - proportion of participants who achieved weight loss of $\geq 5\%$ from baseline. and
 - mean change from randomization in SF-36v2 acute form

- Physical Component Summary score
- Mental Component Summary score
- Physical Functioning domain score
- General Health domain score
- Vitality domain score
- Role-Physical domain score
- Bodily Pain domain score
- Social Functioning domain score
- Role-Emotional domain score
- Mental Health domain score.

The following tertiary/exploratory objectives are also not subject to strong control of the type 1 error rate:

- To compare tirzepatide (pooled cohort of 5 mg, 10 mg, and 15 mg) to insulin lispro (U100) TID when added to insulin glargine (U100), with or without metformin at 52 weeks for:
 - mean change in lipids (total cholesterol, high-density lipoprotein [HDL-C], low-density lipoprotein [LDL-C], very low-density lipoprotein [VLDL-C], and triglycerides [TG]) from baseline
 - mean change in waist circumference from baseline
 - mean change in body mass index (BMI) from baseline, and
 - patient-reported outcomes
 - EQ-5D-5L
 - Ability to Perform Physical Activities of Daily Living (APPADL)
 - Impact of Weight on Self-Perception (IW-SP).

4.4. Safety Objectives

To evaluate the safety of tirzepatide (pooled cohort of 5 mg, 10 mg, and 15 mg) QW to insulin lispro TID, when added to insulin glargine (U100), with or without metformin at 52 weeks, and at the end of the safety follow-up period, with respect to the following outcomes:

- treatment-emergent adverse events (TEAEs)
- serious adverse events (SAEs)
- early discontinuation of study intervention (tirzepatide or insulin lispro [U100]) due to adverse events (AEs)

[figure not shown]
- adjudicated pancreatitis
- serum calcitonin
- incidence of treatment-emergent antidrug antibodies (ADAs) and systemic hypersensitivity reactions
- mean change in systolic and diastolic blood pressure and heart rate from baseline
- incidence of initiation of rescue therapy for severe, persistent hyperglycemia, and
- occurrence of hypoglycemic episodes.

5. Study Design

5.1. Summary of Study Design

Study I8F-MC-GPHD (GPHD) is a Phase 3b, multicenter, multinational, open-label, parallel-arm, randomized study, which will assess the safety and efficacy of the addition of tirzepatide (5 mg, 10 mg, or 15 mg QW) versus insulin lispro (U100) for change from baseline in HbA1c in participants with type 2 diabetes mellitus (T2DM) inadequately controlled on insulin glargine (U100) with or without metformin over a 52-week treatment.

Figure GPHD.5.1 illustrates the study design.

Abbreviations: QW = once weekly; TID = three times a day.

Figure GPHD.5.1. Illustration of study design for clinical protocol I8F-MC-GPHD.

Study Period I (Screening and Insulin Optimization)

Visit 1 (Screening)

The purpose of screening procedures at Visit 1 is to establish initial eligibility and to obtain blood samples for laboratory assessments needed to confirm eligibility at Visit 2. Participants who meet all applicable inclusion criteria and none of the applicable exclusion criteria at Visit 1 will continue on their prestudy therapy doses between Visit 1 and Visit 2.

Visit 2 to Visit 6 (Insulin Glargine Optimization)

At Visit 2, the screening laboratory results from Visit 1 will be reviewed. A dilated fundoscopic exam will be performed between Visit 2 and Visit 3 as results are required to confirm eligibility. If calcitonin results are unavailable, then Visit 2 can proceed and calcitonin results can be reviewed later before randomization occurs.

At Visit 2, all participants should switch their pre-trial basal insulin therapy to Lilly provided insulin glargine (U100) and discontinue other oral glucose lowering agents except metformin. Between Visit 2 up to Visit 6, participants should continue taking the same dose and formulation of metformin ≥ 1500 mg/day, if used, unless any contraindication or clinical condition develops that requires adjustment of the dose. Participants should receive optimal therapy or clinical care for diabetes related comorbidities.

[Figure GPHD.5.2](#) illustrates how participants who are eligible would proceed for insulin glargine optimization.

For all participants who are eligible until completion of Visit 2, the investigator will determine whether the participant belongs to **Group 1** or **Group 2** at Visit 2 and follow insulin optimization plan accordingly. **Group 1** consists of participants who are on pre-trial basal insulin regimen of insulin glargine (U100) daily at bedtime \pm metformin (≥ 1500 mg/day). **Group 2** consists of participants who are on a pre-trial basal insulin regimen **other than** insulin glargine (U100) daily at bedtime \pm metformin (≥ 1500 mg/day) or require discontinuation of sulfonylureas (SU) and/or dipeptidyl peptidase-4 inhibitors (DPP4i). Participants from **Group 1** will continue on their current dose of insulin glargine (U100) \pm metformin (≥ 1500 mg/day) between Visit 2 and Visit 3, and measure fasting blood glucose (FBG) everyday between Visit 2 and Visit 3. Participants from **Group 2** will initiate optimization of insulin glargine (U100) for 10 weeks, starting at Visit 2 and up to Visit 6.

At Visit 3, participants from **Group 1** who do not require further insulin glargine (U100) optimization (**Group 1A**) (ie, if median of last 3 FBG is ≤ 125 mg/dL [≤ 6.9 mmol/L] at Visit 3) should have their randomization visit (Visit 6) within 2 weeks after Visit 3. These participants will skip Visits 4 and 5. Participants from **Group 1** who require further insulin glargine (U100) optimization (**Group 1B**) (ie, if median of last 3 FBG is > 125 mg/dL [> 6.9 mmol/L] at Visit 3) will initiate optimization of insulin glargine (U100) for 9 weeks, starting at Visit 3 and up to Visit 6.

For **Group 1B** and **Group 2** participants , the insulin glargine (U100) dose optimization and self-monitoring blood glucose (SMBG) plan should be targeted at a FBG of 100 to 125 mg/dL (5.6 to 6.9 mmol/L, inclusive) and determined by the investigator per clinical judgement. An additional blood sample will be collected for **Group 1B** and **Group 2** participants for HbA1c assessment at Visit 5. Only participants with Visit 5 HbA1c $\geq 7.5\%$ (58 mmol/mol) to $\leq 11\%$ (97 mmol/mol) will be eligible for randomization.

Those participants who discontinue the study prior to Visit 6 do not need to perform an early termination visit and safety follow-up visit.

[figure not shown]

Figure GPHD.5.2. Flowchart to ascertain need for insulin glargine (U100) optimization.

Study Period II (52-week treatment period)

Visit 6 (Randomization)

At Visit 6, participants will undergo all required baseline study procedures (including the collection of all baseline laboratory measures, vital signs, electrocardiogram (ECG), and questionnaires) prior to randomization and prior to injecting their first dose of study intervention, tirzepatide or insulin lispro (U100).

All participants, randomized to either tirzepatide or insulin lispro (U100) TID, will **reduce their dose of insulin glargine (U100) by 30% at Visit 6** to reduce the potential risk of hypoglycemia and safely introduce tirzepatide or insulin lispro (U100) and follow titration instructions for insulin glargine (U100) treatment. Participants will follow dose-escalation schemes for tirzepatide or titration instructions for insulin lispro (U100) thereafter.

End of Visit 6 to Visit 23 (Post-Randomization)

Insulin Glargine (U100)

For participants in the tirzepatide arms, dose of insulin glargine (U100) will remain unchanged after the initial 30% dose reduction at Visit 6 until 4 weeks after randomization (ie, until Visit 10) except for safety reasons (ie, hypoglycemia/severe hyperglycemia). Participants will initiate insulin glargine (U100) titration after Visit 10 per protocol-defined Insulin Glargine (U100) Titration Algorithm.

For participants in the insulin lispro (U100) arm, participants will initiate titration of insulin glargine (U100) after Visit 6 per protocol-defined Insulin Glargine (U100) Titration Algorithm.

For insulin glargine (U100) titration, all participants should adjust insulin glargine (U100) dose weekly. Participants will be instructed to adjust insulin glargine (U100) doses to a targeted FBG of 100 to 125 mg/dL (5.6 to 6.9 mmol/L). If the participant achieves the target FBG per titration algorithm for 2 consecutive weeks and the dose of insulin glargine (U100) is less than 10 units, investigator may choose to temporarily interrupt insulin glargine (U100) injection.

Tirzepatide

For participants randomized to tirzepatide 5 mg QW arm, the starting dose of tirzepatide will be 2.5 mg QW for 4 weeks, followed by an increase to 5 mg QW, for the duration of the study. For the 10 mg arm, the starting dose of tirzepatide will be 2.5 mg QW for 4 weeks, then the dose will be increased by 2.5 mg every 4 weeks (2.5 to 5 to 7.5 to 10 mg) until the 10 mg dose is reached and maintained for the duration of the study. For the 15 mg arm, the starting dose of tirzepatide will be 2.5 mg QW for 4 weeks, then the dose will be increased by 2.5 mg every 4 weeks (2.5 to 5 to 7.5 to 10 to 12.5 to 15 mg) until the 15 mg dose is reached and maintained for the duration of the study.

Insulin Lispro

Participants randomized to insulin lispro (U100) arm will start administrating 4 U of insulin lispro, prior to the 3 most significant meals of the day. Participants should adjust insulin lispro

(U100) dose twice-weekly until Week 24 after randomization (ie, Visit 20). After Visit 20, the investigator may choose to reduce the frequency of insulin lispro (U100) dose adjustment to once weekly per clinical judgement.

Participants will be instructed to adjust insulin lispro (U100) doses to a target pre-meal and bedtime SMBG of 100 to 125 mg/dL (5.6 to 6.9 mmol/L) according to the protocol defined Insulin Lispro (U100) Titration Algorithm. If the participant achieves the glycemic goal per titration algorithm for 2 consecutive weeks and the dose of insulin lispro (U100) for corresponding meal is less than 4 units, investigator may choose to temporarily interrupt insulin lispro (U100) injections related to that mealtime.

Study Period III (Safety Follow-up Period)

Visit 801

All participants who complete the treatment period are required to complete Visit 801, a safety follow-up visit, approximately 4 weeks after their last treatment visit. Participants discontinuing the study early and performing an early termination (ET) visit will also be asked to perform the safety follow-up visit, so that the safety follow-up visit will be their final visit. During the safety follow-up period, participants will not receive study intervention (tirzepatide or insulin lispro [U100]). Initiation of new antihyperglycemic therapy for the safety follow-up period will not be classified as “rescue therapy.” Insulin glargine (U100) use will be permitted during the period.

5.2. Sample Size Determination

Although the primary objective of the trial is to demonstrate that the pooled cohort of tirzepatide (5 mg, 10 mg, and 15 mg) QW is noninferior to insulin lispro (U100) TID, relative to the primary endpoint (mean change in HbA1c from baseline to 52 weeks), sample size selection is guided by establishing noninferiority of each tirzepatide dose, tested against insulin lispro (U100), relative to the primary endpoint (mean change in HbA1c from baseline to 52 weeks). The power is assessed based on the following assumptions:

- the evaluation of noninferiority of each individual tirzepatide dose to insulin lispro (U100) will be conducted at one-sided 0.025 significance level, using a two-sample t-test
- a 0% difference in mean change in HbA1c from baseline to 52 weeks for each tirzepatide arm compared with insulin lispro (U100)
- a common standard deviation (SD) of 1.3% (accounting for increase in SD due to the inclusion of data on rescue medications and after premature treatment discontinuation and imputation of missing data)
- a noninferiority margin of 0.3%, and
- 1:1:1:3 randomization ratio (chosen to optimize power for establishing primary objective and to optimize safety comparison between pooled tirzepatide cohort versus insulin lispro).

On the basis of these assumptions, randomizing 1182 participants in a 1:1:1:3 ratio to tirzepatide 5 mg (197 participants), tirzepatide 10 mg (197 participants), tirzepatide 15 mg (197 participants) and insulin lispro (U100) (591 participants) provides 80% power to demonstrate noninferiority of each tirzepatide dose to insulin lispro (U100). Furthermore, this sample size will ensure 97% power to achieve the primary objective: establishing noninferiority of the pooled cohort of tirzepatide (5 mg, 10 mg, and 15 mg) compared to insulin lispro (U100), using a 2-sample t-test at 1-sided significance level of 0.025, provided a 0.0% difference in mean change in HbA1c from baseline to 52 weeks for the pooled cohort of tirzepatide doses compared with insulin lispro (U100), a common SD of 1.3% and noninferiority margin of 0.3%.

5.3. Method of Assignment to Treatment

Approximately 1182 participants who meet all criteria for enrollment will be randomized to one of the study treatment arms at Visit 6. Assignment to treatment arms will be determined by a computer-generated random sequence using an interactive web response system (IWRS).

Participants will be randomized in a 1:1:1:3 ratio to receive 5 mg tirzepatide, 10 mg tirzepatide, 15 mg tirzepatide, or insulin lispro (U100). The randomization will be stratified by country, pre-randomization HbA1c concentration ($\leq 8.5\%$, $> 8.5\%$ [≤ 69 , > 69 mmol/mol]), and baseline metformin use (Yes/No).

6. A Priori Statistical Methods

6.1. Populations for Analyses

For purposes of analysis, [Table GPHD.6.1](#) defines the following analysis populations/data sets.

Table GPHD.6.1. Analysis Populations/Data Sets

| Population/Data Set | Description |
|---|--|
| Screened population | All participants who sign informed consent |
| Enrolled population | All participants who are exposed to at least 1 dose of insulin glargine (U100) after Visit 2 |
| Randomized population | All participants who are randomly assigned a treatment arm |
| Safety Population | All randomly assigned participants who are exposed to at least 1 dose of study drug (tirzepatide or insulin lispro [U100]). |
| Modified intention-to-treat (mITT) population | All randomly assigned participants who are exposed to at least 1 dose of study drug (tirzepatide or insulin lispro [U100]), excluding inadvertently enrolled participants who have discontinued study drug for that reason. |
| Lead-in analysis set (LAS) | Data obtained during Study Period I, after first dose of insulin glargine (U100) after Visit 2 and prior to the first dose of tirzepatide or insulin lispro (U100) (or Visit 6 date if the dose date is missing). |
| Efficacy analysis set (EAS) | Data obtained during Study Period II from the mITT population, excluding data after initiating rescue antihyperglycemic medication or early discontinuation of study drug (tirzepatide: last dose date + 7 days; insulin lispro (U100): last dose date). |
| Full analysis set (FAS) | All available data obtained during Study Period II, regardless of adherence to study drug or initiation of rescue antihyperglycemic medication. |
| Safety analysis set (SS) | All available data obtained during Study Periods II and III regardless of adherence to study drug or initiation of new antihyperglycemic medication. |

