4.1.1. Overview of Study Periods

On all designated fasting office visits, study participants must report to the site in a fasting condition, after approximately 8 hours without eating, drinking (except water), or performing any significant physical activity. If a participant is adversely affected by the fasting condition, they are allowed to eat; however, specific study procedures need to be completed while fasting.

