6.1.2.2.2. Insulin Lispro (U100)

Participants randomized to insulin lispro (U100) arm will start administering **4 U** of insulin lispro (U100), prior to the 3 most significant meals of the day, that is, the 3 largest meals.

Participants are expected to eat 3 main meals per day (for example, morning/breakfast, midday/lunch, and evening/dinner) on a regular basis.

At Visit 6, site personnel will provide appropriate training on instruction for use of the insulin pen for injection of insulin lispro (U100). The training can be provided using a demonstration device, if available. This training will be repeated at subsequent visits, as needed.

Participant should adjust insulin lispro (U100) dose twice weekly until Week 24 after randomization (that is, Visit 20). After Visit 20, the investigator may choose to reduce the frequency of insulin lispro (U100) dose adjustment to once weekly per clinical judgment and pre-meal/bedtime SMBG values.

The dose adjustment for a particular injection of the day of insulin lispro (U100) will be based upon the median of the previous 3 SMBG values for each corresponding referenced time point as indicated in [Table 8](#).

Table 8. Insulin Lispro (U100) Dose Adjustments

For dose adjustment of insulin lispro (U100) at...	use...
First meal (e.g. pre-breakfast dose)	pre-second meal SMBG values (e.g. pre-lunch SMBG values)
Second meal (e.g. pre-lunch dose)	pre-third meal SMBG values (e.g. pre-dinner SMBG values)
Third meal (e.g. pre-dinner dose)	bedtime SMBG values

If 2 SMBG values are available, then the average value will be calculated and will be used to adjust the dose. If none or only 1 value is available, the participant should contact the investigator site for instructions on adjusting insulin lispro (U100) dose.

Participants will be instructed to adjust insulin lispro (U100) doses to a target pre-meal and bedtime SMBG of 100 to 125 mg/dL (5.6 to 6.9 mmol/L), inclusive according to [Table 9](#).

Table 9. Insulin Lispro (U100) Titration Algorithm

If median pre-meal/bed-time blood glucose is...		Then adjust dose of insulin lispro (U100) for respective meal by...
mg/dL	mmol/L	
≤70	≤3.9	Decrease by 2 units
71 to 99	4.0 to 5.5	Decrease by 1 unit
100 to 125	5.6 to 6.9	No adjustment
≥126	≥7.0	Increase by 2 units

Insulin lispro (U100) dose should be decreased by 2 units (for a particular meal) for any dose adjustment, if participant experienced any episode that either,

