8.1. Efficacy Assessments

8.1.1. Primary Efficacy Assessments

The primary efficacy measurement in this study is mean change in HbA1c values from baseline to 52 weeks, as determined by the central laboratory. Blood samples for HbA1c measurements will be collected at specific in-clinic visits as summarized in the SoA (Section 1.3.).

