9.3. Populations for Analyses

Table 15. Populations for Analyses

Population	Description
Screened participants	All participants who sign informed consent.
Randomized participants	All participants who are randomly assigned to a treatment arm.
mITT population	All randomly assigned participants who are exposed to at least 1 dose of study intervention, that is, tirzepatide or insulin lispro (U100). In the event of a treatment error, participants will be analyzed according to the treatment they were randomized.
EAS	Data obtained during Study Period II from the mITT population, excluding data after initiating rescue antihyperglycemic medication or stopping study intervention.
FAS	Data obtained during Study Period II from the mITT population, regardless of adherence to study intervention or initiation of rescue antihyperglycemic medication.
SS	Data obtained during Study Periods II or III from the mITT population, regardless of adherence to study intervention or initiation of rescue antihyperglycemic medication.

Abbreviations: EAS = efficacy analysis set; FAS = full analysis set; mITT = modified intention-to-treat; SS = safety analysis set.

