6.10. Treatment Exposure and Compliance

A listing of patients randomized but not receiving study treatment will be provided, if applicable. The listing will include patient identification, randomized treatment arm, and the reason for not receiving study treatment (if the data is available).

A summary of duration to follow-up (defined as time in days from date of randomization to date of safety follow-up, date of early study discontinuation or date of death) and duration on study treatment (defined as time in days from first dose date to last dose date plus 7 days for tirzepatide arms; from first dose date to last dose date for insulin lispro (U100) arm) will be provided by treatment.

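### The efficacy analysis set gives tirzepatide a 7-day allowance after the last dose and lispro none, so a lispro participant who stops at a fasting visit can lose that visit's on-treatment HbA1c and weight

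*SAP*

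**What the plan says.** SAP 6.1 (Table GPHD.6.1) takes the EAS from Study Period II and removes data after rescue or after "early discontinuation of study drug (tirzepatide: last dose date + 7 days; insulin lispro (U100): last dose date". SAP 6.10 uses the same two windows for time on treatment: "last dose date plus 7 days for tirzepatide arms; from first dose date to last dose date for insulin lispro (U100) arm".

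Protocol 9.3 defines the EAS with no day window for either arm: "excluding data after initiating rescue antihyperglycemic medication or stopping study intervention". SAP 6.2 describes the efficacy estimand as efficacy before study intervention is discontinued.

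Three other statements determine how the SAP rule works in practice:

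- Protocol 6.1.2.2.2 has lispro injected "prior to the 3 most significant meals of the day, that is, the 3 largest meals".
- Protocol 4.1.1 has participants arrive at designated visits "after approximately 8 hours without eating, drinking (except water), or performing any significant physical activity".
- Protocol 8.1.1 states "Blood samples for HbA1c measurements will be collected at specific in-clinic visits as summarized in the SoA". In the schedule (Protocol 1.3, Table 2) the eight post-baseline HbA1c visits are all fasting visits, and all of them include weight.

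The SAP revision history adds "Updated baseline definition as time is not collected in GPHD eCRF", so the cut is probably applied to dates, not clock times.

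**The concern.** HbA1c and weight measured at the visit where a participant stops reflect the preceding weeks on treatment. They belong to the efficacy estimand and are not data after stopping in the protocol's sense. The SAP's date rule can still discard them for lispro while keeping them for tirzepatide.

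The EAS feeds a mixed model for repeated measures (MMRM) that treats missing values as missing at random (SAP 6.4, 6.12.1.1). If the decision to stop is related to the participant's current glycaemia, the value at that visit is what makes the assumption tenable. Once it is dropped, stopping depends on a value the model no longer sees. The model's implied Week 52 mean for lispro can then be biased, with no matching loss for tirzepatide participants dosed on schedule. The same data support the efficacy-estimand analyses of weight and of HbA1c below 7%.

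**Working it through.** **The plan's own figures.** The documents attach no number to this rule. The nearest figures are the power statements in SAP 5.2 (SD 1.3, margin 0.3, true difference 0, one-sided 0.025).

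- Pooled: SE = 1.3 × √(1/591 + 1/591) = 0.0756; 0.3/0.0756 = 3.97; power = Φ(3.97 − 1.96) = 0.978 (stated 97%).
- Each dose: SE = 1.3 × √(1/197 + 1/591) = 0.107; 0.3/0.107 = 2.80; power = Φ(2.80 − 1.96) = 0.80 (stated 80%).

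Both reproduce, and the EAS window enters neither.

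**Date logic.** A visit on day V is kept if V ≤ last dose date + window.

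| Arm and window | Last dose on V | V−1 | V−7 | V−8 or earlier |
|---|---|---|---|---|
| Lispro, +0 (SAP) | kept | excluded | excluded | excluded |
| Lispro, +1 | kept | kept | excluded | excluded |
| Tirzepatide, +7 (SAP) | kept | kept | kept | excluded |

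A participant who arrives fasting for a morning visit and takes no further lispro will usually have a last dose dated V−1, the previous evening's meal.

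**How many.** The documents give no discontinuation rate. Assume 5–20% of lispro participants stop early and 25–100% of those stops fall at an HbA1c visit. The number losing one visit runs from 591 × 0.05 × 0.25 ≈ 7 to 591 × 0.20 × 1 ≈ 118. The 8% and 15% used below correspond to about 47 and 89 participants.

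**How large, by simulation.** All settings here are assumptions:

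- 200,000 profiles over eight visits, residual SD 1.2.
- Stopping possible at visits 2–7, with log-odds linear in the current value and the intercept set to give 8% or 15% stopping.
- Within-person correlation either compound symmetry (0.5, 0.7) or first-order autoregressive (0.7 to 0.95).
- A stopper's Week 52 value replaced by its conditional normal expectation given the retained values.

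Keeping the stop visit gives a bias of about 0.00. Dropping it shifts the lispro Week 52 mean, in percentage points, as follows:

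| Stopping follows | Log-odds per SD | 8% stop | 15% stop |
|---|---|---|---|
| High HbA1c, strong | 1.5 | −0.01 to −0.024 | −0.02 to −0.04 |
| High HbA1c, weak | 0.5 | −0.004 to −0.009 | −0.007 to −0.016 |
| Low HbA1c, moderate | −0.7 | about +0.01 | +0.01 to +0.02 |
| Unrelated | 0 | 0 | 0 |

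The model is symmetric, so low-HbA1c stopping at log-odds 1.5 would mirror the first row.

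**Hand check.** Shift ≈ share affected × average departure of the lost value from its model prediction × fraction carried to Week 52. With a departure of 0.5 and half carried over, 0.08 × 0.5 × 0.5 = 0.02 and 0.15 × 0.5 × 0.5 = 0.0375, in line with the strong-dependence row. An extreme corner (20% affected, a full 1.0-point average departure, 80% carried) gives 0.16, but it needs every stop to fall at an HbA1c visit and all the departures to run one way.

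**Scale.** 0.04/0.3 = 13% of the margin and 0.04/0.0756 ≈ 0.5 of the pooled SE. 0.006/0.3 = 2% of the margin.

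**Direction.** The contrast is tirzepatide minus lispro. A lispro mean that is too low moves the contrast up, against tirzepatide; one that is too high moves it down, in tirzepatide's favour.

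**The case against.** Several points stand and limit the size of this concern.

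- **The loss is conditional.** A lispro dose dated on the visit day keeps the visit. The documents do not say how the last dose date is recorded for someone who stops at a visit. Tirzepatide participants who stop after three or more missed weekly doses (Protocol 6.6.3, 7.1) lose the visit too.
- **Strong dependence is hard to support.** Log-odds of 1.5 per SD is an odds ratio of about 4.5. HbA1c goes to a central laboratory, so the result is unlikely to be known when the participant stops; self-monitored glucose carries only part of that signal. Protocol 8.3.6.2 manages high glucose by titration and then add-on rescue, and hyperglycaemia is not named among the discontinuation reasons in Protocol 7.1.
- **Many stops lose no HbA1c.** Six post-randomization contacts are by telephone, and in-clinic Visits 8, 12 and 21 have no HbA1c.
- **Unequal windows have a rationale.** Seven days is one tirzepatide dosing interval. A reader might infer that different windows are an error in themselves. They are not; the gap is that lispro has no equivalent allowance.
- **Scope is narrow.** The FAS has no such cut, and SAP 6.12 points to the treatment-regimen analysis for regulatory use.

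The defence that the bias is conservative stands only in part. It holds if stopping follows high HbA1c. Protocol 2.1 names hypoglycaemia as a concern with basal-bolus insulin, and stopping at low HbA1c reverses the sign. None of these points gives a reason to discard a value that the estimand includes.

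**Conclusion.** The asymmetry is real and avoidable. For some lispro early discontinuers the literal rule in Table GPHD.6.1 removes an on-treatment HbA1c and weight that the efficacy estimand and the protocol's EAS would keep. What is lost is a value before Week 52 in the efficacy-estimand analyses. Completers' Week 52 values are untouched, because the cut applies only to early discontinuation.

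With 8–15% of lispro participants stopping at an HbA1c visit, the shift in the lispro Week 52 mean is about −0.006 to −0.04 if stopping follows high HbA1c. It is about +0.01 to +0.02 if stopping moderately follows low HbA1c, and zero if the two are unrelated. The stopping rate, the timing of stops, the strength of dependence and the within-person correlation are all assumed; the documents supply none of them.

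A reader might infer that the rule biases the trial towards noninferiority, or that every lispro participant who stops loses a visit. The documents support neither. The sign depends on why people stop, the loss depends on how the last dose is dated, and the shift is small beside the 0.3 margin. This is a minor correction.

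**What to change.** In SAP Table GPHD.6.1, make one of two changes to the data cut:

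- set the lispro cut for HbA1c and weight at last dose date + 1 day, one dosing day to parallel one dosing week; or
- state that assessments at the visit where discontinuation is decided count as on-treatment in both arms.

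The second option also covers tirzepatide participants whose last dose was more than 7 days before that visit, so its wording should say whether that is intended. Either way, the SAP should state how the last dose date is assigned when a participant stops at a visit.

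The cost is one phrase in a table and the matching derivation. Sample size, power and participant management do not change. There is one small downside: if + 1 day were applied to every measure, an occasional next-day fasting glucose or self-monitored value taken off lispro could enter the EAS. Limiting the window to HbA1c and weight avoids that, because one day cannot make either meaningfully off-treatment. Running the efficacy-estimand analysis under both cuts would show directly whether the choice matters.
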